6.13.3. Deaths, Other Serious Adverse Events, and Other Notable Adverse Events

Overviews of adverse events will be presented for the Placebo-Controlled period and the Delayed-Start period, respectively, including within each period the number and percentage of subjects who died, experienced serious adverse events, experienced adverse events leading to study discontinuation, and experienced treatment-emergent adverse events. Treatment groups will be compared in the Placebo-Controlled period using Fisher's Exact Test.

Events of the major adverse cardiovascular event type (MACE) that are blindly evaluated by external independent consultants will be summarized and listed.

In addition, the proportion of subjects within specific clusters of TEAEs will be summarized and treatment comparisons will be conducted using Fisher's Exact Test. Clusters will be created from MedDRA High Level Group Terms (HLGTs) and MedDRA SMQ's.

 Table AZET.SAP.2.
 Adverse Events of Special Interest

AE Groups of Interest (Clusters)	MedDRA High Level Group Terms (HLGTs)
Nervous System Disorders	Neuromuscular Disorders HLGT
	Demyelination SMQ
	Peripheral Neuropathy SMQ
Eye Disorders	Retinal disorders SMQ
Skin Disorders	Sub-group A:
	Epidermal and Dermal Conditions HLGT (excluding sub-group B terms)
	Sub-group B (Hypopigmentation-related events):
	Hypopigmentation disorders HLT
	Pigmentation changes, NEC HLT
	Preferred terms: 'hair depigmented', 'eyelash discolouration', 'iris hypopigmentation', 'eye colour change', 'lip colour altered', 'lip discolouration', 'hair colour changes', 'achromotrichia aquired', 'poliosis'
Liver Disorders	Drug related hepatic disorders - comprehensive search SMQ
Cardiovascular-type events – Arrhythmic	Arrhythmia related investigations, signs and symptoms SMQ
	Cardiac arrhythmia terms (incl bradyarrhythmias and tachyarrhythmias) SMQ
	TdP/QT prolongation SMQ
Cardiovascular-type events - Ischemic	Ischaemic heart disease SMQ
Cardiovascular-type events - Stroke	Central nervous system vascular disorders SMQ
Cardiovascular-type events – including orthostatic hypotension	Decreased and Nonspecific Blood Pressure Disorders and Shock HLGT

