### 9.4.9.1. Adverse Events of Special Interest

Adverse events of special interest will include:

- Adverse eye effects including retina (Section 9.4.7)
- Adverse skin effects including rash (Section 9.4.9.3) and hypopigmentation (Section 9.4.8)
- Peripheral nervous system, central nervous system and muscle effects
- Liver toxicity (Section 9.4.9 and Section 8.1.1)
- Cardiovascular (CV)-type events (including, but not limited to, orthostatic hypotension and QT prolongation) (Section 9.4.9.2)

The topics listed above, as well as new topics which may be subsequently determined by the Sponsor, will be subject to enhanced surveillance activities. Additionally, the topics above will be analyzed for presentation in the Clinical Study Report in accordance with the Statistical Analysis Plan (SAP).

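### The special-interest adverse event table has no row for general central nervous system events or non-retinal eye events, although the protocol names CNS and eye effects as topics to be analysed

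*SAP*

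**What the plan says.** **Protocol 9.4.9.1** gives the special-interest topics. Two matter here: "Peripheral nervous system, central nervous system and muscle effects" and "Adverse eye effects including retina (Section 9.4.7" (the cross-reference is to the eye examination section). The protocol then says that "the topics above will be analyzed for presentation in the Clinical Study Report", in accordance with the SAP.

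**SAP 6.13.3** plans a summary of the proportion of subjects in specific clusters of treatment-emergent adverse events, with Fisher's exact test. Table AZET.SAP.2 defines the clusters:

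- Nervous system: "Neuromuscular Disorders HLGT", "Demyelination SMQ" and "Peripheral Neuropathy SMQ".
- Eye: "Retinal disorders SMQ" and nothing else.
- A standardised query for CNS vascular disorders sits under the stroke cluster.
- Skin sub-group B contains a few eye terms that concern pigment (iris, eye colour, eyelash).

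**SAP 6.13.2** tabulates all treatment-emergent events, serious events and events leading to discontinuation by preferred term within SOC, with Fisher's exact test. It does not say whether the SOC line itself is counted and tested.

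**SAP 6.1** says that, after the stop for futility, no test will be read as statistically significant. Low p-values only mark results of possible interest.

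**The concern.** The protocol names CNS effects on an equal footing with peripheral and muscle effects, and it words the eye topic to include the retina without being limited to it. The SAP table is narrower on both, gives no reason, and uses row titles (nervous system disorders, eye disorders) that suggest full cover. A reader of the study report could take those rows as the answer to the protocol's topics when most of the CNS topic and the non-retinal eye topic are outside them.

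The drug is described in Protocol 3.1 as brain-permeable, so CNS tolerability is a natural safety question. A modest central effect may show up as small excesses in many different preferred terms. A special-interest cluster exists to gather such terms into one comparison; without it, each term is judged alone on few events.

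**Working it through.** **Step 1. Protocol topics against planned analyses.**

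| Topic (Protocol 9.4.9.1) | Cluster in Table AZET.SAP.2 | Other planned analyses | Left without a pooled comparison |
|---|---|---|---|
| Peripheral nervous system | Peripheral neuropathy; neuromuscular | Terms within SOC | – |
| CNS | Demyelination; CNS vascular (under stroke) | Suicidality composites with Fisher's test (SAP 6.13.8.1); ARIA-E and ARIA-H by chi-square (SAP 6.13.7); terms within SOC | General CNS adverse events |
| Muscle | Neuromuscular, at least in part | Terms within SOC | Cannot be judged: the term content of the grouping is not in the documents |
| Eye, including retina | Retinal; a few pigment terms under skin | Visual acuity, intraocular pressure, slit-lamp and fundus summaries (SAP 6.13.8.3); terms within SOC | Other non-retinal eye adverse events |

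**Step 2. What pooling could gain (illustration only).** The documents give no event rates, so every rate below is an assumption. The group size is the planned 633 (SAP 5.2), which follows from 554/(1 − 0.25 × 0.50) = 633.1. The level is two-sided 0.05 (Protocol 10.3.4). Exact power is the sum, over all event counts x and y, of Bin(x; 633, p1) × Bin(y; 633, p2), taken where Fisher's two-sided p is at most 0.05.

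| Assumed rates, active v placebo | Reading | Power |
|---|---|---|
| 10% v 5% | One cluster, no unrelated events | 91% |
| 1.0% v 0.5% | Each of ten equal terms | 9.8% |
| 8% v 5% | One cluster, no unrelated events | 54% |
| 0.8% v 0.5% | Each of ten equal terms | 4.5% |

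The 10% figure takes it that no patient has two of the terms. If the ten terms occur independently, the cluster rates are 1 − 0.99^10 = 9.6% and 1 − 0.995^10 = 4.9%, and pooled power is 88%.

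**Step 3. What a broad cluster could lose.** A row built from most of a SOC also collects events unrelated to the drug. Suppose 20% of patients in each group have such an event, independently. Then 10% v 5% becomes 1 − 0.80 × 0.90 = 28% v 1 − 0.80 × 0.95 = 24%, and power falls to about 34%. With 30% background it is 37% v 33.5%, and power is about 24%.

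Under these assumptions the pooled row is still more sensitive than any single term (34% or 24% against 10%), but the advantage shrinks as background events are added.

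**The case against.** The case for leaving the table alone has several parts.

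- **The events are not untested.** A reader might infer from the table that CNS events are never pooled or compared. The documents do not support that. SAP 6.13.2 tests every preferred term, and demyelination, CNS vascular, suicidality and ARIA findings are all analysed as groups. Whether SOC totals are tested is unstated, not ruled out. This stands.
- **Rare terms are not hidden.** A reader might also infer that terms below 2% drop out of view. They do not: the list of events in at least 2% of subjects is an additional table beside the full one. This stands.
- **Eye effects are examined directly.** The protocol's eye topic points to the eye examination, and SAP 6.13.8.3 summarises acuity, pressure, slit-lamp and fundus results, including new abnormal findings. This covers much of the topic. It does not compare reported non-retinal eye adverse events between groups, and that section states no test.
- **The protocol leaves the content to the SAP.** It fixes no MedDRA groupings, and its risk section (3.3) names retinal changes but no general CNS risk. That may explain the narrower rows. But the topic list is the protocol's own, and the SAP neither covers it nor says why not.
- **Nothing confirmatory depends on it.** Under SAP 6.1 power at 0.05 is only a rough gauge. This stands, and it limits the point to display and signal detection.
- **Ten tests give ten chances.** With independent terms at 9.8% each, the chance that at least one reaches 0.05 is 1 − (1 − 0.0976)^10 = 64%. But one such term among the many in the full table is hard to tell from a chance finding.

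**Conclusion.** The gap is real and modest. Two topics named in Protocol 9.4.9.1, CNS effects and eye effects beyond the retina, lack a special-interest cluster that matches them. Outside the partial analyses in the table above, such events are seen only by preferred term within SOC, and a SOC-level count or test is not stated. Even a tested nervous-system SOC line would mix central and peripheral events, so it would not isolate the CNS topic.

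Muscle should not be called missing: the neuromuscular grouping covers it at least in part, and the documents do not allow more to be said.

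The power figures show direction only. They assume the event rates, independence where stated, and the planned 633 per group; because the trial stopped early, actual exposure will be shorter. About 91% against 10% describes a cluster with no unrelated events, and 34% is the pooled figure with 20% background. The conclusion rests on the mismatch between the protocol's list and the SAP's table, not on these figures.

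**What to change.** In Table AZET.SAP.2:

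1. Add a CNS row: the Nervous system disorders SOC, excluding terms already in the peripheral neuropathy and neuromuscular groupings.
2. Add an Eye disorders SOC row, with "Retinal disorders SMQ" kept as a sub-group.
3. Apply the Fisher comparison already used for the clusters, in the Placebo-Controlled period only, since SAP 6.13 excludes between-treatment p-values for the Safety-DS population.
4. State which grouping is meant to cover muscle effects.
5. Keep all existing narrow clusters, because a broad row can dilute a specific signal. Say that rows may overlap.
6. Amend the sentence before the table, which now builds clusters only from high level group terms and standardised queries, so that SOC-based rows are allowed.

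If the rows are not added, the minimum is to state in SAP 6.13.2 that SOC-level counts are presented with Fisher's test, and to justify the narrower clusters against the protocol's list.

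The cost is two rows and a few sentences, run with an analysis already planned, plus a few more unadjusted, hypothesis-generating p-values. Protocol 10.3.4 and SAP 6.1 already accept unadjusted p-values. SAP Version 3 already revises the skin cluster and is to be approved before final unblinding, so the change belongs there.

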6.13.4. Clinical Laboratory Evaluations

Laboratory measures will be analyzed both as continuous data (change from baseline) and categorical or ordinal data (proportions of treatment-emergent abnormalities).

If there are multiple records of laboratory measurements at a baseline or post-baseline visit, the latest record will be used.

Summaries and analyses of continuous data (change from baseline) will use both conventional and International System of Units (SI units).

For the Placebo-controlled period, change from baseline to post-baseline visits will be compared between treatment groups using an MMRM model. For each lab analyte, the rank-transformation will be applied to the change from baseline for all subjects and all visits prior to analysis. Similarly, an independent rank transformation will be applied to the baseline values prior to analysis. The model for the fixed effects will include terms for: baseline, treatment, visit, and the treatment-by-visit interaction. This analysis will be done separately for each lab analyte. For the Delayed-Start period, mean change from baseline to post-baseline visits will be summarized.

For the Placebo-Controlled period, treatment differences in the proportions of subjects with treatment-emergent high or treatment emergent low or treatment-emergent abnormal laboratory values at (1) anytime and (2) each post-baseline visit will be assessed using Fisher's Exact Test. Treatment-emergent high or low abnormalities will be calculated using SI units. For each lab analyte, only those subjects who were low or normal at baseline and have at least one post-baseline measurement will be included in the denominator when calculating the proportion of subjects with treatment-emergent high values. Similarly, only subjects who were high or normal at baseline and have at least one post-baseline measurement will be included in the denominator when calculating the proportion of subjects with treatment-emergent low values. In addition, treatment differences in the proportion of subjects who were normal at baseline and change to abnormal high or abnormal low values at any post-baseline visit will be summarized. For the Delayed-Start period, the proportions will be summarized.

A second categorical analysis will be conducted on laboratory analytes. This analysis is considered a PCS analysis and will use limits typically wider than the first categorical analysis. Abnormal criteria for these treatment-emergent PCS changes are presented in **Error! Reference source not found.**

For urinalysis parameters, baseline to post-baseline shifts will be summarized at each visit. For the Placebo-Controlled period, likelihood ratio chi-square tests will be used to compare increase, no change and decrease shifts in urinalysis parameters between treatment groups at each visit.

For all laboratory analytes, frequencies of subjects with notable changes (that is, increases or decreases of a prespecified amount unique to each analyte) from baseline to each postbaseline visit were also summarized for all subjects and stratified by low, normal, or high at baseline.

The proportion of subjects with treatment-emergent clinically significant changes from a low value or normal value at all baseline at any time in ALT and total bilirubin will be summarized by treatment group. Clinically significant changes of interest are: $ALT \ge 3$ x upper limit of

normal (ULN) and total bilirubin ≥ 2 x ULN, AST ≥ 3 x ULN, ALT ≥ 5 x ULN, ALT ≥ 10 x ULN, and total bilirubin ≥ 2 x ULN. Additionally, Hy's Law analysis will be conducted by comparing treatment groups with regard to the proportion of patients with (ALT ≥ 3 x ULN OR AST ≥ 3 x ULN) AND total bilirubin ≥ 2 x ULN. Comparisons between treatment groups will be carried out using Fisher's Exact test in the Placebo-Controlled period. When criteria are met for hepatic evaluation and completion of the hepatic safety case report form (CRF), investigators are required to answer a list of questions pertaining to the patient's history, relevant pre-existing medical conditions, and other possible causes of liver injury. A listing of the information collected on the hepatic-safety CRF will be generated.

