**Optional** 

(tested at the discretion of the investigator or if mandated by local regulatory authority)

Human immunodeficiency virusa

Abbreviations: HDL = High-density lipoproteins; LDL = Low-density lipoproteins; PCR = polymerase chain reaction; RBC = red blood cells; WBC = white blood cells.

- a At screening only.
- b Done at all other times besides screening.
- c At screening only in patients with suspected or past history of Hepatitis B.
- d At screening only in patients with suspected or past history of Hepatitis C.
- e At screening, Week 26, Week 52, and Week 78 (or final study visit) only for the Placebo-Controlled period as well as Week 104, Week 130, and Week 156 (or final study visit) only for the Delayed-Start period.

Note: Laboratory values outside the reference limit suspected to be of any clinical significance will be repeated. Patients for whom suspected clinical significance is confirmed will either not be enrolled or, if already enrolled, will be followed until normalization or for as long as the Investigator considers necessary. Additional laboratory tests may be performed for safety reasons if judged appropriate by the investigator. See Section 9.4.4 for information regarding the recording of AEs based on laboratory tests. All laboratory samples will be analyzed using routine methods per the central laboratory, as referenced in the Laboratory Manual for this study.

For blood volume, see Appendix 5.

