6.13.5. Vital Signs and Other Physical Findings

Vital sign measurements and weight will be analyzed using continuous data (change from baseline) and categorical data (proportion of potentially clinically significant changes).

If there are multiple records of vital sign or weight measurements at baseline or a postbaseline visit, the last record will be used. Summary statistics will be presented for observed values at baseline and for change from baseline results at each scheduled postbaseline visit. Systolic and diastolic blood pressure and pulse (collected in sitting position), orthostatic diastolic and orthostatic systolic blood pressures and orthostatic pulse (measurement after 5 minutes in the supine position minus that after 2 and 5 minutes in the standing position), temperature, and weight by treatment group for all subjects in the safety population will be summarized.

With the large number of visits at which vital signs are scheduled to be measured, the MMRM model is not suitable for the change from baseline comparison of treatments. In the Placebo-Controlled period change from baseline to each post-baseline visit at which vital signs are taken will be assessed using an ANCOVA model with treatment and as independent factors and baseline value and age as covariates in the model. This analysis will be done separately for each vital sign parameter and weight. In the Delayed-Start period, these changes will be summarized.

The incidence of treatment-emergent abnormal high or low vital signs and weight will be presented by treatment group and visit. Treatment-emergent vital sign evaluations are defined for evaluations collected after the initiation of study medication. Abnormal criteria for postbaseline vital signs and weight are presented in Appendix 5. Any vital sign or weight meeting the criteria will be considered abnormal. In the Placebo-Controlled period, treatment differences in the proportion of subjects with treatment-emergent abnormal high or low vital signs and weight will be assessed between treatment groups using Fisher's Exact test at (1) any time and (2) by post-baseline visit.

For each vital sign at each post-baseline visit, only subjects who had a baseline result and had a nonmissing result at that post-baseline visit will be included in the denominator when computing the proportion of subjects with treatment-emergent high, low, or abnormal values.

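### SAP 6.13.4 uses only the latest laboratory record at a visit for threshold counts as well as mean changes, so a normal same-visit repeat removes the abnormal value that prompted it

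*SAP*

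**What the plan says.** SAP 6.13.4 sets its scope in the opening sentence: "Laboratory measures will be analyzed both as continuous data (change from baseline) and categorical or ordinal data (proportions of treatment-emergent abnormalities"). The record rule follows directly: "If there are multiple records of laboratory measurements at a baseline or post-baseline visit, the latest record will be used". Nothing limits it to one type of analysis.

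The categorical outputs in the same section are:

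- treatment-emergent high, low or abnormal results, where "treatment-emergent abnormal laboratory values at (1) anytime and (2) each post-baseline visit will be assessed using Fisher's Exact Test";
- a second threshold analysis, of which the SAP says "This analysis is considered a PCS analysis and will use limits typically wider than the first categorical analysis";
- liver thresholds, where changes "at any time in ALT and total bilirubin will be summarized by treatment group", together with a Hy's Law comparison.

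None of these has its own rule for choosing between records.

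The note to Protocol Appendix 2 says when a test is repeated: "Laboratory values outside the reference limit suspected to be of any clinical significance will be repeated". If the suspicion is confirmed in an enrolled patient, that patient "will be followed until normalization or for as long as the Investigator considers necessary".

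**The concern.** Taking the latest record is a sensible way to get one value per patient per visit for a mean change. It suits a count of patients who ever crossed a limit less well, because the second record is not there at random. It is usually there because the first value was abnormal and looked important. A normal first value would not be repeated under Appendix 2, so the rule can turn an abnormal visit into a normal one but will seldom do the reverse.

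The stakes are highest for the liver. Protocol 3.3 names elevated liver enzymes as a potential risk, and Protocol 9.4.9.1 lists liver toxicity as an event of special interest. The liver-multiple and Hy's Law tables are meant to show such a signal by treatment group. A short-lived elevation that has settled by the repeat is the kind of event that the rule can remove from them.

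**Working it through.** The documents give no laboratory abnormality rate, repeat rate or safety power, so there is no planned figure to reproduce. The check is a comparison of texts, followed by an illustration on assumed rates.

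**Step 1: where second records come from.** The schedules in Protocol Tables 2.2 and 2.3 have one laboratory entry per visit. A second record must come from a repeat under Appendix 2 or from an added safety test. For the liver, the trigger and the counting limit coincide: Protocol 9.4.9 starts hepatic monitoring at ALT of at least 3 x ULN or total bilirubin of at least 2 x ULN, and SAP 6.13.4 counts patients at those same levels. A value that qualifies for the table is therefore among those most likely to be followed by another.

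**Step 2: one patient (assumed values).** ALT is 4.2 x ULN at a visit and 0.9 x ULN on repeat, with no abnormal result at any other visit.

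- Repeat filed under the same visit, latest record used: 0.9 is below 3, so the patient is in neither the by-visit nor the any-time count.
- Same filing, worst value used: 4.2 is above 3, so the patient is counted.
- Repeat filed as a separate unscheduled record: 4.2 remains the scheduled visit's only value, and the patient is counted under either rule.

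**Step 3: what a loss would do to a group comparison (assumed rates).** Inputs from the documents: 633 patients per group as planned (Protocol 10.1) and a two-sided 0.05 level for safety tests (Protocol 10.3.4). Assumed: true any-time rates of 3% on one dose and 1% on placebo, and a fraction f of abnormal patients in each arm whose only abnormal value is replaced. Expected count = 633 x rate x (1 - f). For f = 0 this is 633 x 0.03 = 19.0 and 633 x 0.01 = 6.3. Power is for Fisher's exact test, by summing the binomial probabilities of all outcomes with p < 0.05.

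| f in both arms | Expected patients, drug vs placebo | Risk difference | Risk ratio | Power |
|---|---|---|---|---|
| 0 | 19.0 vs 6.3 | 2.0 points | 3 | 0.67 |
| 25% | 14.2 vs 4.7 | 1.5 points | 3 | 0.52 |
| 50% | 9.5 vs 3.2 | 1.0 point | 3 | 0.33 |
| 75% | 4.7 vs 1.6 | 0.5 points | 3 | 0.11 |

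With other assumed rates and f = 50%, power falls from 0.61 to 0.26 (2% vs 0.5%) and from 0.81 to 0.46 (5% vs 2%).

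Equal fractional loss leaves the risk ratio at 3. The ratio moves only if the loss differs by arm. With f = 50% on drug and 25% on placebo (again assumed), the counts are 9.5 and 4.7 and the ratio falls to about 2.

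**Step 4: practice elsewhere in the SAP.** The skin section (6.13.8.2) uses the maximum value during treatment. The eye section (6.13.8.3) uses the maximum value and the worst assessment. The C-SSRS section (6.13.8.1) uses the maximum ideation score, and 6.13.2 tabulates adverse events by maximum severity. The laboratory counts depart from this pattern, and no reason is given.

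**Step 5: baseline.** The rule also applies at baseline, so a normal repeat can turn an abnormal baseline into a normal one and change who enters the treatment-emergent denominators. The liver-threshold analysis already uses a different standard: it requires a low or normal result at all baseline assessments.

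**The case against.** The strongest reply is that the rule acts only on several records at one visit, and that liver follow-up may not be filed that way. Protocol Appendix 5 calls hepatic monitoring unscheduled. Appendix 4 gives it a separate panel, which a local laboratory may run, while scheduled tests go to the central vendor (Protocol 9.4.4). SAP 6.1.1 and 6.1.2 recognise unscheduled measurements as distinct. SAP 6.3.1 admits safety data from visits where they were not scheduled to all analyses other than the repeated measures models, though that sentence is written for patients who discontinue early. If repeats are filed as separate unscheduled records, the abnormal value stays in both counts. This stands as a limit on the finding. It does not remove it, because the documents do not say how repeats are filed, and a liver count should not depend on an unstated convention.

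A second reply is that the event is visible elsewhere. Treatment-emergent adverse events, the Liver Disorders cluster (SAP 6.13.2 and 6.13.3) and the hepatic case report form listing (SAP 6.13.4) may show it. This stands in part. Protocol 9.4.4 requires an adverse event report for clinically significant findings that result in a diagnosis, and a listing is not a comparison between groups. A reader might infer that the abnormal value vanishes from all safety reporting. It does not; the point concerns the laboratory abnormality counts.

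Third, the trial was stopped for futility, and SAP 6.1 says that no test will be interpreted as statistically significant. That lowers the weight of the power column above. The counts and differences are still reported, and under SAP 6.12.2.1 safety is the only type of data summarized for the Delayed-Start period.

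A reader might also carry the argument over to vital signs, because SAP 6.13.5 has a parallel rule: "If there are multiple records of vital sign or weight measurements at baseline or a postbaseline visit, the last record will be used". The documents do not support a bias claim there. Appendix 2 covers laboratory values only, the repeat blood pressure reading in exclusion criterion 26 concerns screening, and the 2- and 5-minute standing readings in Protocol 9.4.2 are scheduled.

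**Conclusion.** The point holds for the laboratory abnormality counts. As written, SAP 6.13.4 lets a normal same-visit repeat remove an abnormal result from that visit's count, and from the any-time count unless another visit is abnormal. The loss runs one way because repeats are prompted by abnormal values. It lowers counts, risk differences and power.

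The size is unknown. It depends on how many repeats are filed under the same visit and how many are normal, and the documents give neither. The figures in the working rest on assumed rates and show direction and sensitivity only. They do not estimate how many ALT elevations of 3 or 5 x ULN would be missed.

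A reader might go further and conclude that the comparison with placebo is shown to be biased toward no harm. That does not follow. Equal fractional loss leaves the risk ratio unchanged, and the documents do not show that the loss differs by arm. Such a bias would arise if elevations on drug resolve on repeat more often than those on placebo.

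**What to change.** In SAP 6.13.4:

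- limit the latest-record rule to the change-from-baseline analyses;
- for the any-time treatment-emergent, PCS, liver-multiple and Hy's Law counts, use the worst value across all post-baseline records in the period, whether scheduled, repeat or unscheduled;
- for by-visit counts, use the worst value within the visit;
- align the baseline rule for these counts with the standard already used for the liver thresholds, which looks at all baseline assessments.

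For Hy's Law, also state whether the transaminase and bilirubin values must be concurrent. The SAP does not say, and worst values taken separately could combine results from different dates.

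The same wording could go into 6.13.5 for consistency only.

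The cost is SAP text and a programming change; no new data are needed. The downside is that some spurious single abnormal values will be counted, in all arms.
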